### 7.1.5.4 Follow-up Visits

Subjects who discontinue trial treatment for a reason other than disease progression will move into the Follow-Up Phase and should be assessed every 12 weeks ( $\pm$  2 weeks) by radiologic imaging to monitor disease status. After 1 year, the imaging time point will occur every 16 weeks ( $\pm$  2 weeks). Every effort should be made to collect information regarding disease status until the start of new anti-neoplastic therapy, disease progression, death, end of the study or if the subject begins retreatment with pembrolizumab as detailed in Section 7.1.5.5. Information regarding post-study anti-neoplastic treatment will be collected if new treatment is initiated.

Subjects who are eligible to receive retreatment with pembrolizumab according to the criteria in Section 7.1.5.5 will move from the follow-up phase to the Second Course Phase when they

experience disease progression. Details are provided in Section 7.1.5.5 – and the Study Flow Chart (Table 6) for Retreatment.

#### 7.1.5.4.1 Survival Follow-up

Once a subject experiences confirmed disease progression or starts a new anti-cancer therapy, the subject moves into the survival follow-up phase and should be contacted by telephone every 12 weeks to assess for survival status until death, withdrawal of consent, or the end of the study, whichever occurs first.

#### 7.1.5.5 Second Course Phase (Retreatment Period)

Subjects who stop pembrolizumab with SD or better may be eligible for up to one year of additional pembrolizumab therapy if they progress after stopping study treatment. This retreatment is termed the Second Course Phase of this study and is only available if the study remains open and the subject meets the following conditions:

- **Either**
  - Stopped initial treatment with pembrolizumab after attaining an investigator-determined confirmed CR according to RECIST 1.1, and
    - Was treated for at least 24 weeks with pembrolizumab before discontinuing therapy
    - Received at least two treatments with pembrolizumab beyond the date when the initial CR was declared

**OR**

- Had SD, PR or CR and stopped pembrolizumab treatment after 18 doses of study therapy for reasons other than disease progression or intolerability

**AND**

- Experienced an investigator-determined confirmed radiographic disease progression after stopping their initial treatment with pembrolizumab
- Did not receive any anti-cancer treatment since the last dose of pembrolizumab
- Has a performance status of 0 or 1 on the ECOG Performance Scale
- Demonstrates adequate organ function as detailed in Section 5.1.2

**C** Confidential

- Female subject of childbearing potential should have a negative serum or urine pregnancy test within 72 hours prior to receiving retreatment with study medication.
- Female subject of childbearing potential should be willing to use 2 methods of birth control or be surgically sterile, or abstain from heterosexual activity for the course of the study through 120 days after the last dose of study medication (Reference Section 5.7.2). Subjects of child bearing potential are those who have not been surgically sterilized or have been free from menses for > 1 year.
- Male subject should agree to use an adequate method of contraception starting with the first dose of study therapy through 120 days after the last dose of study therapy.
- Does not have a history or current evidence of any condition, therapy, or laboratory abnormality that might interfere with the subject's participation for the full duration of the trial or is not in the best interest of the subject to participate, in the opinion of the treating investigator.

Subjects who restart treatment will be retreated at the same dose and dose interval as when they last received pembrolizumab. Treatment will be administered for up to one additional year.

Visit requirements are outlined in Section 6.0 – Trial Flow Chart.

## 7.2 Assessing and Recording Adverse Events

An adverse event is defined as any untoward medical occurrence in a patient or clinical investigation subject administered a pharmaceutical product and which does not necessarily have to have a causal relationship with this treatment. An adverse event can therefore be any unfavorable and unintended sign (including an abnormal laboratory finding, for example), symptom, or disease temporally associated with the use of a medicinal product or protocol-specified procedure, whether or not considered related to the medicinal product or protocol-specified procedure. Any worsening (i.e., any clinically significant adverse change in frequency and/or intensity) of a preexisting condition that is temporally associated with the use of the Merck's product, is also an adverse event.

Changes resulting from normal growth and development that do not vary significantly in frequency or severity from expected levels are not to be considered adverse events. Examples of this may include, but are not limited to, teething, typical crying in infants and children and onset of menses or menopause occurring at a physiologically appropriate time.

[REDACTED] protocol-specified procedure, whether investigational (including placebo or active comparator medication) or marketed, manufactured by, licensed by, provided by or distributed by [REDACTED] human use.

[REDACTED] IRB  
IRB ID: [REDACTED]  
Approval Date: [REDACTED]  
Expiration Date: [REDACTED]

Adverse events may occur during the course of the use of [REDACTED] product in clinical trials or within the follow-up period specified by the protocol, or prescribed in clinical practice, from overdose (whether accidental or intentional), from abuse and from withdrawal.

Adverse events may also occur in screened subjects during any pre-allocation baseline period as a result of a protocol-specified intervention, including washout or discontinuation of usual therapy, diet, placebo treatment or a procedure.

Progression of the cancer under study is not considered an adverse event unless it is considered to be drug related by the investigator.

All adverse events will be recorded from the time the consent form is signed through 30 days following cessation of treatment and at each examination on the Adverse Event case report forms/worksheets. The reporting timeframe for adverse events meeting any serious criteria is described in section 7.2.3.1.

#### **7.2.1 Definition of an Overdose for This Protocol and Reporting of Overdose to the Sponsor and to Merck**

For purposes of this trial, an overdose of pembrolizumab will be defined as any dose of 1,000 mg or greater ( $\geq 5$  times the indicated dose). No specific information is available on the treatment of overdose of pembrolizumab. Appropriate supportive treatment should be provided if clinically indicated. In the event of overdose, the subject should be observed closely for signs of toxicity. Appropriate supportive treatment should be provided if clinically indicated.

If an adverse event(s) is associated with ("results from") the overdose of a Merck product, the adverse event(s) is reported as a serious adverse event, even if no other seriousness criteria are met.

If a dose of [REDACTED] product meeting the protocol definition of overdose is taken without any associated clinical symptoms or abnormal laboratory results, the overdose is reported as a non-serious Event of Clinical Interest (ECI), using the terminology "accidental or intentional overdose without adverse effect."

All reports of overdose with and without an adverse event must be reported within 24 hours to the Sponsor and within 2 working days hours to Merck Global Safety. (Attn: Worldwide Product Safety; [contact])

#### **7.2.2 Reporting of Pregnancy and Lactation to the Sponsor and to Merck**

Although pregnancy and lactation are not considered adverse events, it is the responsibility of investigators or their designees to report any pregnancy or lactation in a subject (spontaneously reported to them), including the pregnancy of a male subject's female partner that occurs during the trial or within 120 days of completing the trial, or 30 days following cessation of treatment if the subject initiates new anticancer therapy, whichever

subjects and female partners of male subjects who become pregnant must be followed to the completion/termination of the pregnancy. Pregnancy outcomes of spontaneous abortion, missed abortion, benign hydatidiform mole, blighted ovum, fetal death, intrauterine death, miscarriage and stillbirth must be reported as serious events (Important Medical Events). If the pregnancy continues to term, the outcome (health of infant) must also be reported.

Such events must be reported within 24 hours to the Sponsor and within 2 working days to [REDACTED]

### 7.2.3 Immediate Reporting of Adverse Events to the Sponsor and to Merck

#### 7.2.3.1 Serious Adverse Events

A serious adverse event is any adverse event occurring at any dose or during any use of Merck's product that:

- Results in death;
- Is life threatening;
- Results in persistent or significant disability/incapacity;
- Results in or prolongs an existing inpatient hospitalization;
- Is a congenital anomaly/birth defect;
- Is a new cancer (that is not a condition of the study);
- Is associated with an overdose;
- Is an other important medical event

Refer to Table 6 for additional details regarding each of the above criteria.

Progression of the cancer under study is not considered an adverse event unless it results in hospitalization or death.

Any serious adverse event, or follow up to a serious adverse event, including death due to any cause other than progression of the cancer under study that occurs to any subject from the time the consent is signed through 90 days following cessation of treatment, or the initiation of new anti-cancer therapy, whichever is earlier, whether or not related to [REDACTED] must be reported within 24 hours to the Sponsor-Investigator (report [REDACTED] with MedWatch 3500A form attached, please see DCP for additional reporting direction). The Sponsor-Investigator will report event to [REDACTED] within 24 hours of becoming aware of event.

Non-serious Events of Clinical Interest will be forwarded to [REDACTED] and will be handled in the same manner as SAEs.

Additionally, any serious adverse event, considered by an investigator who is a qualified physician to be related to [REDACTED] that is brought to the attention of the investigator at [REDACTED]

any time outside of the time period specified in the previous paragraph also must be reported immediately to the Sponsor and to [REDACTED]

**SAE reports and any other relevant safety information are to be forwarded to the [REDACTED] Global Safety facsimile number: [REDACTED]**

A copy of all 15 Day Reports and Annual Progress Reports is submitted as required by FDA, European Union (EU), Pharmaceutical and Medical Devices agency (PMDA) or other local regulators. Investigators will cross reference this submission according to local regulations to the Merck Investigational Compound Number (IND, CSA, etc.) at the time of submission. Additionally investigators will submit a copy of these reports to [REDACTED] at the time of submission to FDA. Sponsor-Investigator is responsible for communication to the FDA.

All subjects with serious adverse events must be followed up for outcome.

#### 7.2.3.2 Events of Clinical Interest

Selected non-serious and serious adverse events are also known as Events of Clinical Interest (ECI) and must be recorded as such on the Adverse Event case report forms/worksheets and reported within 24 hours to the Sponsor-Investigator (report to RCINJ via OnCore with MedWatch 3500A form attached, please see DCP for additional reporting direction). The Sponsor-Investigator will report event to [REDACTED] hours of becoming aware of event (At [REDACTED] of clinical interest for this trial include [REDACTED]

1. An overdose of [REDACTED] product, as defined in Section 7.2.1 - Definition of an Overdose for This Protocol and Reporting of Overdose to the Sponsor, that is not associated with clinical symptoms or abnormal laboratory results.
2. An elevated AST or ALT lab value that is greater than or equal to 3X the upper limit of normal and an elevated total bilirubin lab value that is greater than or equal to 2X the upper limit of normal and, at the same time, an alkaline phosphatase lab value that is less than 2X the upper limit of normal, as determined by way of protocol-specified laboratory testing or unscheduled laboratory testing.\*

\*Note: These criteria are based upon available regulatory guidance documents. The purpose of the criteria is to specify a threshold of abnormal hepatic tests that may require an additional evaluation for an underlying etiology. The trial site guidance for assessment and follow up of these criteria can be found in the Investigator Trial File Binder (or equivalent).

3. Additional adverse events:

A separate guidance document has been provided entitled "Event of Clinical Interest Guidance Document" (previously entitled, "Event of Clinical Interest and Immune-Related Adverse Event Guidance Document"). This document provides guidance regarding identification, evaluation and management of ECIs and irAEs.

ECIs (both non-serious and serious adverse events) identified in this guidance document from the date of first dose through 90 days following cessation of treatment, or 30 days after the initiation of a new anticancer therapy, whichever is earlier, need to be reported within 24 hours to the Sponsor and within 2 working days to [REDACTED], regardless of attribution to study treatment, consistent with standard SAE reporting guidelines.

Subjects should be assessed for possible ECIs prior to each dose. Lab results should be evaluated and subjects should be asked for signs and symptoms suggestive of an immune-related event. Subjects who develop an ECI thought to be immune-related should have additional testing to rule out other etiologic causes. If lab results or symptoms indicate a possible immune-related ECI, then additional testing should be performed to rule out other etiologic causes. If no other cause is found, then it is assumed to be immune-related.

#### 7.2.4 Evaluating Adverse Events

An investigator who is a qualified physician will evaluate all adverse events according to the NCI Common Terminology for Adverse Events (CTCAE), version 4.0. Any adverse event which changes CTCAE grade over the course of a given episode will have each change of grade recorded on the adverse event case report forms/worksheets.

All adverse events regardless of CTCAE grade must also be evaluated for seriousness.

Table 13 Evaluating Adverse Events

An investigator who is a qualified physician, will evaluate all adverse events as to:

|                           |   |   |
|---------------------------|---|---|
| V4.0
Grading           | Grade 1   | Mild; asymptomatic or mild symptoms; clinical or diagnostic observations only; intervention not indicated.  |
|                           | Grade 2   | Moderate; minimal, local or noninvasive intervention indicated; limiting age-appropriate instrumental ADL.  |
|                           | Grade 3   | Severe or medically significant but not immediately life-threatening; hospitalization or prolongation of hospitalization indicated; disabling; limiting self-care ADL.  |
|                           | Grade 4   | Life threatening consequences; urgent intervention indicated.   |
|                           | Grade 5   | Death related to AE   |
| Seriousness               | A serious adverse event is any adverse event occurring at any dose or during any use of Merck product that  |   |
|                           | ‡Results in death, or   |   |
|                           | ‡Is life threatening; or places the subject in the view of the investigator, at immediate risk of death from the event as it occurred (Note: This does not include an adverse event that, had it occurred in a more severe form, might have caused death); or   |   |
|                           | ‡Results in a persistent or significant disability/incapacity (substantial disruption of one's ability to conduct normal life functions), or  |   |
|                           | ‡Results in or prolongs an existing inpatient hospitalization (hospitalization is defined as an inpatient admission, regardless of length of stay, even if the hospitalization is a precautionary measure for continued observation. (Note: Hospitalization [including hospitalization for an elective procedure] for a preexisting condition which has not worsened does not constitute a serious adverse event.); or  |   |
|                           | ‡Is a congenital anomaly/birth defect (in offspring of subject taking the product regardless of time to diagnosis), or  |   |
|                           | Is a new cancer; (that is not a condition of the study) or  |   |
|                           | Is an overdose (whether accidental or intentional). Any adverse event associated with an overdose is considered a serious adverse event. An overdose that is not associated with an adverse event is considered a non-serious event of clinical interest and must be reported within 24 hours.  |   |
|                           | Other important medical events that may not result in death, not be life threatening, or not require hospitalization may be considered a serious adverse event when, based upon appropriate medical judgment, the event may jeopardize the subject and may require medical or surgical intervention to prevent one of the outcomes listed previously (designated above by a ‡).   |   |
|                           | Record the start and stop dates of the adverse event. If less than 1 day, indicate the appropriate length of time and units   |   |
| Duration                  | Did the adverse event cause the [REDACTED] product to be discontinued?  |   |
| Action taken              | Did the Merck product cause the adverse event? The determination of the likelihood that the Merck product caused the adverse event will be provided by an investigator who is a qualified physician. The investigator's signed/dated initials on the source document or worksheet that supports the causality noted on the AE form, ensures that a medically qualified assessment of causality was done. This initialed document must be retained for the required regulatory time frame. The criteria below are intended as reference guidelines to assist the investigator in assessing the likelihood of a relationship between the test drug and the adverse event based upon the available information |   |
| Relationship to test drug | The following components are to be used to assess the relationship between the [REDACTED] product and the AE; the greater the correlation with the components and their respective elements (in number and/or intensity), the more likely the Merck product caused the adverse event (AE).  |   |
|                           | Exposure  | Is there evidence that the subject was actually exposed to the Merck product such as: reliable history, acceptable compliance assessment (pill count, diary, etc.), expected pharmacologic effect, or measurement of drug/metabolite in bodily specimen?                                |
|                           | Time Course   | Did the AE follow in a reasonable temporal sequence from administration of the Merck product?   |
|                           | Likely Cause  | Is the time of onset of the AE compatible with a drug-induced effect (applies to trials with investigational medicinal product)?
Is the AE not reasonably explained by another etiology such as underlying disease, other drug(s)/vaccine(s), or other host or environmental factors |

[REDACTED] IRB  
 [REDACTED] IRB  
 Approval Date:  
 Expiration Date:

Product: [REDACTED] / No.: [REDACTED] / 0

**C** Confidential

|   |   |
|---|---|
| 
Relationship to [REDACTED] product (continued)
 | 
The following components are to be used to assess the relationship between the test drug and the AE: (continued)
 
Was the [REDACTED] AE resolve or improve?
         If yes, this is a positive dechallenge. If no, this is a negative dechallenge.
         (Note: This criterion is not applicable if: (1) the AE resulted in death or permanent disability; (2) the AE resolved/improved despite continuation of the Merck product; or (3) the trial is a single-dose drug trial; or (4) [REDACTED] (s) is/are only used one time.)
 
Rechallenge
         Was the subject re-exposed to the [REDACTED] in this study?
         If yes, did the AE recur or worsen?
         If yes, this is a positive rechallenge. If no, this is a negative rechallenge.
         (Note: This criterion is not applicable if: (1) the initial AE resulted in death or permanent disability, or (2) the trial is a single-dose drug trial; or (3) [REDACTED] product(s) is/are used only one time).
 NOTE: RECHALLENGE IS PLANNED FOR AN ADVERSE EVENT WHICH WAS SERIOUS AND WHICH MAY HAVE BEEN CAUSED BY THE [REDACTED] PRODUCT, OR IF REEXPOSURE TO THE [REDACTED] PRODUCT POSES ADDITIONAL POTENTIAL SIGNIFICANT RISK TO THE SUBJECT, THEN THE RECHALLENGE MUST BE APPROVED IN ADVANCE BY THE U.S. CLINICAL MONITOR AS PER DOSE MODIFICATION GUIDELINES IN THE PROTOCOL.
         Is the clinical/pathological presentation of the AE consistent with previous knowledge regarding the [REDACTED] product or drug class pharmacology or toxicology?
 |
| 
Consistency with Trial Treatment Profile
       | 
The assessment of relationship will be reported on the case report forms /worksheets by an investigator who is a qualified physician according to his/her best clinical judgment, including consideration of the above elements.
   |
| 
Record one of the following
                    | 
Use the following scale of criteria as guidance (not all criteria must be present to be indicative of a [REDACTED] product relationship).
 
Yes, there is a reasonable possibility of [REDACTED] relationship.
         There is evidence of exposure to the [REDACTED] explained by the Merck product than by another cause.
 
No, there is not a reasonable possibility of [REDACTED] product relationship
         Subject did not receive the [REDACTED] product OR temporal sequence of the AE onset relative to administration of the [REDACTED] product is not reasonable OR there is another obvious cause of the AE. (Also entered for a subject with overdose without an associated AE.)
   |

[REDACTED] IRB  
 [REDACTED] IRB ID:  
 Approval Date:  
 Expiration Date:

### 7.2.5 Sponsor Responsibility for Reporting Adverse Events

All Adverse Events will be reported to regulatory authorities, IRB/IECs and investigators in accordance with all applicable global laws and regulations.

## 8.0 STATISTICAL ANALYSIS PLAN

### 8.1 Statistical Analysis Plan Summary

A schema to evaluate the safety of administering pembrolizumab with chemoradiation (CRT) is provided below. Successive regimens have progressively longer concurrent treatment times going from post radiation, to 2 weeks overlap, to 6 week overlap if tolerated or increase MK-3475 from 1 MGQ 3 WEEKS to 2 mg Q 3 WEEKS. The safety is evaluated through dose limiting toxicity (DLT) consisting of grade 4 pneumonitis. The 3+3 design with dose de-escalation and starting at Regimen 1 will be used to find the maximum tolerated dose (MTD) regimen. After MTD is found, six more patients will be treated at MTD dose regimen for a better evaluation of the safety of the dosing schedule for further study. The details of the 3+3 design with dose de-escalation are shown below.

Day 0 is the start day for chemoradiation (CRT)

Day 42 is the presumed last day of chemoradiation

Table 4: Trial Design

| START of Pembrolizumab    | Day of starting Pembrolizumab | Pembrolizumab Dose | Regimen |
|---------------------------|-------------------------------|--------------------|---------|
| 2-6 WEEKS AFTER CRT       | Day 56-84                     | 100 mg Q3 WEEKS    | -1      |
| 2-6 WEEKS AFTER CRT       | Day 56-84                     | 200 mg Q3WEEKS     | 1       |
| 2 WEEKS BEFORE END OF CRT | Day 28                        | 100 mg Q3WEEKS     | 2       |
| 2 WEEKS BEFORE END OF CRT | Day 28                        | 200 mg Q3WEEKS     | 3       |
| AT START OF CRT           | Day 0                         | 100 mg Q3WEEKS     | 4       |
| At start of CRT           | Day 0                         | 200 mg Q3WEEKS     | 5       |

With starting dose regimen 1, groups of 3 patients will be entered at a dose level:

- If all 3 patients treated at the dose regimen do not have a dose limiting toxicity (DLT), then the dose will be escalated to the next dose regimen.
- If 1/3 patients have DLT, then 3 more patients will be treated at this dose level. If none of these additional patients has DLT, then the dose will be escalated, otherwise three more patients are treated at the prior dose regimen (if at most 3 patients were previously treated at that prior dose regimen).
- If at least 2/3 patients have DLT, then three more patients are treated at the prior dose regimen (if at most 3 patients were previously treated at that prior dose regimen).

The MTD is the dose regimen that 0/6 (or 0/3 if at dose level -1) or 1/6 patient experience DLT; and at least 2/3 or 2/6 patients treated with the next higher dose regimen will have had DLT.

Note: If the escalation occurs at the last dose regimen (Regimen 5), then the MTD is at or above the last dose regimen. If the de-escalation occurs at dose regimen -1 (at least 2 out of 3 patients or at least 2 out of 6 patients have DLT at dose regimen -1), then the MTD is below the dose regimen -1. In either case, the MTD is not determined from the trial. But for the former, the last regimen (Regimen 5) is safe and still can be used safely for further studies.

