## 8.2 Statistical Analysis Plan

The study design is shown in Study Design/Clinical Plan Section. Table 1 gives three different scenarios for the probabilities of toxicity at the dose regimens. In the first scenario, we assume dose-toxicity rates such that the rate is 5% at dose level -1 and increases gradually to 50% at dose regimen 5. In the second scenario, we assume dose-toxicity rates such that the rate is 12% at dose regimen -1 and 50% at dose regimen 5. In the third scenario, the dose-toxicity rate is 3% at dose regimen -1 and increases slowly to 50% at dose regimen 5.

Table 14. Three scenarios of probabilities of toxicity at dose levels

| Dose Regimen | First Scenario of Probability of Toxicity | Second Scenario of Probability of Toxicity | Third Scenario of Probability of Toxicity |
|--------------|---|--|---|
| -1           | 0.05                                      | 0.12                                       | 0.03                                      |
| 1*           | 0.08                                      | 0.15                                       | 0.04                                      |
| 2            | 0.15                                      | 0.21                                       | 0.06                                      |
| 3            | 0.24                                      | 0.28                                       | 0.12                                      |
| 4            | 0.36                                      | 0.38                                       | 0.26                                      |
| 5            | 0.50                                      | 0.50                                       | 0.50                                      |

\*: Starting dose level

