For the secondary objective, Kaplan Meier estimation method is used to estimate the rates of local and distant metastasis-free survival, progression-free survival, and overall survival. The comparisons to the historical controls are performed using one-sample log-rank test. Local and distant metastasis-free survival is defined as the event without recurrence within the radiation field (i.e. local - planning target volume) and outside of the radiation field (i.e. distance - in other parts of the lung) or recurrence in other organs. Progression-free survival is the event without sign of any progression either locally or distantly, measured from the initiation of chemoradiation. Overall survival is the overall longevity of the patient from time of initiation of chemoradiation to time of death.

From Table 1, the probability that a dose regimen will be declared as the MTD is calculated in Table 2. Also included in Table 2 is the target toxicity level (i.e., the probability of toxicity at the MTD, if MTD is determined in the given dose regimen.)

Table 2 shows that most likely the regimen 2 will be declared as MTD under the first toxicity model scenario. For Scenarios 2, Regimens 1 and 2 are likely to be the MTD. For Scenario 3, Regimen 3 is likely to be the MTD. There is less than a 10% chance that the MTD cannot be determined from the trial in all the scenarios (3.3%, 4.4% and 8.2% for the 1st, 2nd and 3rd scenarios, respectively).

Table 15: Three scenarios of P(DLT) at each dose level and probability of MTD for each dose level

| Dose level (i)  | -1   | 1*   | 2    | 3    | 4    | 5    |
|---|------|------|------|------|------|------|
| P(DLT at di)  |      |      |      |      |      |      |
| 8.3 Scenario 1   | 0.05 | 0.08 | 0.15 | 0.24 | 0.36 | 0.50 |
| Scenario 2  | 0.12 | 0.15 | 0.21 | 0.28 | 0.38 | 0.50 |
| Scenario 3  | 0.03 | 0.04 | 0.06 | 0.12 | 0.26 | 0.50 |
| P(declare MTD = Regimen i)  |      |      |      |      |      |      |
| 8.4 Scenario 1   | 0.06 | 0.19 | 0.31 | 0.29 | 0.12 | 0.00 |
| Scenario 2  | 0.17 | 0.27 | 0.27 | 0.19 | 0.07 | 0.00 |
| Scenario 3  | 0.02 | 0.04 | 0.13 | 0.38 | 0.35 | 0.00 |
| P(MTD < Regimen 1) = 0.002, P(MTD ≥ Regimen 5) = 0.031; TTL = 18.3% for 1st scenario  |      |      |      |      |      |      |
| P(MTD < Regimen 1) = 0.026, P(MTD ≥ Regimen 5) = 0.018; TTL = 20.2% for 2nd scenario  |      |      |      |      |      |      |

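### Section 8.1 declares Regimen 5 safe after 0/3 or 1/6 DLTs, which cannot exclude a 50% DLT rate, and Section 8 as written does not trigger the expansion there

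*Combined protocol and SAP*

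**What the plan says.** Section 8.1 sets out a 3+3 design over six regimens, starting at Regimen 1. The DLT is grade 4 pneumonitis.

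- **Escalation.** "If all 3 patients treated at the dose regimen do not have a dose limiting toxicity (DLT), then the dose will be escalated". One DLT in the first three leads to three more patients, and escalation follows if none of those has a DLT. A pass is therefore 0/3 or 1/6.
- **MTD.** "The MTD is the dose regimen that 0/6 (or 0/3 if at dose level -1) or 1/6 patient experience DLT", and the next higher regimen must have shown at least 2/3 or 2/6.
- **Expansion.** "After MTD is found, six more patients will be treated at MTD dose regimen". The stated purpose is a better safety evaluation before further study.
- **Top regimen.** "If the escalation occurs at the last dose regimen (Regimen 5), then the MTD is at or above the last dose regimen". The same Note adds: "In either case, the MTD is not determined from the trial". It then says of this case that "the last regimen (Regimen 5) is safe and still can be used safely for further studies".

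Section 8.2 refers elsewhere for the design: "The study design is shown in Study Design/Clinical Plan Section". That section is not in the supplied text. Section 8.2 also says: "There is less than a 10% chance that the MTD cannot be determined from the trial in all the scenarios", with figures of 3.3%, 4.4% and 8.2%. These include the Regimen 5 outcome.

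**The concern.** The Note makes two statements about one outcome. That the MTD is at or above Regimen 5 and not determined follows from the rule. That the regimen is safe does not: it is a conclusion about the DLT rate drawn from three or six patients.

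Two features apply to Regimen 5 in particular. First, the MTD definition asks for six patients at Regimens 1 to 4 (0/3 is allowed only at Regimen -1), whereas three DLT-free patients are enough for the statement about Regimen 5. Second, the expansion is conditional on an MTD being found. Regimen 5 has no higher regimen, so it can never meet the MTD definition, and Table 15 gives it probability 0.00. Read literally, the regimen recommended for further studies is the one whose added safety evaluation is not triggered.

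At stake is a safety claim carried into later studies on data that leave a very high DLT rate open.

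**Working it through.** **Inputs.** Escalation and MTD rules from Section 8.1; DLT rates from Table 14. For Regimens 1 to 5 these are 0.08, 0.15, 0.24, 0.36, 0.50 (Scenario 1); 0.15, 0.21, 0.28, 0.38, 0.50 (Scenario 2); 0.04, 0.06, 0.12, 0.26, 0.50 (Scenario 3).

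**1. Does 0/3 count as a pass at Regimen 5?** The chance of passing a regimen with DLT rate p is

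(1−p)³ + 3p(1−p)²·(1−p)³ = (1−p)³ + 3p(1−p)⁵.

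The chance of reaching Regimen 5 is the product over Regimens 1 to 4:

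- Scenario 1: 0.9369 × 0.8138 × 0.6215 × 0.3781 = 0.179
- Scenario 2: 0.8138 × 0.6869 × 0.5358 × 0.3428 = 0.103
- Scenario 3: 0.9826 × 0.9627 × 0.8715 × 0.5783 = 0.477

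At p = 0.50 the chance of passing Regimen 5 is 0.125 + 0.0469 = 0.1719. If six patients with at most one DLT were required, it would be (1−p)⁶ + 6p(1−p)⁵ = 7/64 = 0.1094. Expected patients at Regimen 5, once reached, are 3 + 3 × 0.375 = 4.125 in the first case and 3 + 3 × 0.5 = 4.5 in the second. Expected DLTs are half of these.

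| Scenarios 1 / 2 / 3 | Printed | 0/3 passes | Six required |
|---|---|---|---|
| P(MTD ≥ Regimen 5), Table 15 | 0.031 / 0.018 / 0.082 | 0.0308 / 0.0176 / 0.0819 | 0.0196 / 0.0112 / 0.0521 |
| Expected patients at Regimen 5, Table 16 | 0.7 / 0.4 / 2.0 | 0.74 / 0.42 / 1.97 | 0.81 / 0.46 / 2.15 |
| Expected DLTs at Regimen 5, Table 16 | 0.37 / 0.21 / 0.98 | 0.370 / 0.212 / 0.983 | 0.40 / 0.23 / 1.07 |

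The printed figures match only with 0/3 as a pass. Full enumeration of the design on that reading also gives the printed total expected sample sizes of 15.8, 14.1 and 18.1.

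**2. How much of the outcome rests on three patients?** At p = 0.50, 0.125 / 0.1719 = 72.7%. In absolute terms, 0/3 accounts for 0.0224 / 0.0128 / 0.0596 and 1/6 for 0.0084 / 0.0048 / 0.0223.

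**3. What do the data exclude?** One-sided 95% exact (Clopper-Pearson) upper bounds:

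- 0/3: solve (1−p)³ = 0.05, so p = 63.2%.
- 1/6: solve (1−p)⁶ + 6p(1−p)⁵ = 0.05, so p = 58.2%.
- For comparison, 0/6 gives 39.3%.

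Both results that count as a pass leave 50% inside the bound.

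**4. How often would a pass occur at other true rates?** Given that Regimen 5 is reached:

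| True DLT rate at Regimen 5 | Rule as written | Six required |
|---|---|---|
| 50% (SAP) | 17.2% | 10.9% |
| 40% (assumed) | 30.9% | 23.3% |
| 30% (assumed) | 49.4% | 42.0% |

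**5. What would the expansion add?** At a 50% rate, six further patients show at least two DLTs with probability 57/64 = 0.89; at an assumed 30% the figure is 0.58. With no further DLT, 0/3 becomes 0/9 (bound 28%) and 1/6 becomes 1/12 (bound 34%). These are favourable cases.

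**6. Does the maximum of 42 settle the expansion?** No. The 36 patients before expansion include six at Regimen -1, which is reached only by stepping down. A path ending with a pass at Regimen 5 uses at most 5 × 6 = 30, or 36 with the expansion.

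**The case against.** The strongest reply is that the Note itself says the MTD is not determined, so the safety statement may mean no more than that Regimen 5 met the escalation rule. No assignment or analysis in Section 8 depends on it. That is a fair reading of intent, but the sentence says more than that, and it speaks of use in further studies.

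Second, wide bounds are a property of any 3+3 design. The 58% bound after 1/6 is the same evidence Section 8.1 accepts for an MTD at Regimens 1 to 4 before expansion. This stands. Only the sufficiency of 0/3 and the untriggered expansion are specific to Regimen 5.

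Third, Section 8.1 is a summary, and the design section that Section 8.2 names is not in the supplied text. A reader might infer that the plan denies Regimen 5 an expansion. The documents do not support that: the missing section may provide for it, and the expansion's stated purpose would fit Regimen 5 equally well. Only Section 8 as written can be judged.

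Fourth, a reader might set the 50% rate against the TTL figures of 18.3%, 20.2% and 15.9% and conclude that the plan breaches its own tolerance limit. It does not. Section 8.2 defines TTL as the toxicity probability at the MTD when one is determined. It is a computed output that leaves this very outcome out, and the supplied text states no maximum acceptable DLT rate.

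Finally, the 50% is a scenario input, not an estimate, so nothing here shows that Regimen 5 is in fact unsafe.

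**Conclusion.** The concern holds in limited form. After a pass at Regimen 5, the plan may say that the escalation rule was met and that the MTD is at or above Regimen 5 and not determined. It cannot call the regimen safe: the upper bounds are 63% after 0/3 and 58% after 1/6, above the 50% assumed there in every SAP scenario.

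The outcome is uncommon in those scenarios (1.8% to 8.2%). It would be more frequent if Regimen 5 were less toxic than assumed, but the claim would then be less wrong.

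The bounds rest only on the counts and independent patients. The probabilities rest on the Table 14 rates and the Section 8.1 rules as written. The point about the safety wording is firm. The point about the expansion supports a request for clarification only.

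**What to change.** **1. Reword the Note in Section 8.1.** Replace the safety statement with text such as:

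> Regimen 5 met the escalation rule. The MTD is at or above Regimen 5 and is not determined. The number of DLTs among patients treated at Regimen 5 will be reported with its one-sided 95% exact upper confidence bound.

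This costs no patients. The downside is a less favourable statement about Regimen 5.

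**2. Reconcile the expansion sentence, the MTD definition and the Note.** State whether the six-patient evaluation and the expansion apply when Regimen 5 passes. The choice is the sponsor's.

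- *Expansion only:* six more patients after a pass, or 0.18 / 0.11 / 0.49 on average over all trials (6 × 0.0308, 0.0176, 0.0819).
- *Both:* nine more after 0/3 (three to complete six, then six) or six more after 1/6. The net change in expected sample size is about 0.28 / 0.16 / 0.74, including trials that fail the added cohort. A path that passes at Regimen 5 stays within 36 patients.

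If the six-patient evaluation is applied, recompute Tables 15 and 16 in full. The figures that change include:

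| Scenarios 1 / 2 / 3 | New value |
|---|---|
| P(MTD ≥ Regimen 5) | 0.020 / 0.011 / 0.052 |
| P(MTD = Regimen 4) | 0.127 / 0.071 / 0.375 |
| P(MTD = Regimen 3), Scenario 3 | 0.39 (printed 0.38) |
| TTL | about 18.4% / 20.3% / 16.2% |
| MTD cannot be determined | 2.1% / 3.7% / 5.2% |
| Expected patients at Regimen 5 | 0.8 / 0.5 / 2.1 |
| Expected DLTs at Regimen 5 | 0.40 / 0.23 / 1.07 |
| Total expected patients, before expansion | 15.9 / 14.2 / 18.4 |

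The DLT totals and percentages in Table 16 change as well.
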